**D. Interim Analyses for Safety and Futility**

Interim analyses will begin after 10 patients have been enrolled. Monitoring will then be performed every 10 patients to ensure that patients are exhibiting reasonable toxicity and efficacy rates to continue with the trial. Patients who receive treatment less than 8 weeks will still be counted in toxicity and futility monitoring as long as they received at least 1 dose of the study drug. For patients already on statins, this means the patient must have started the combination. For patients who are starting on atorvastatin, patients will count as long as they received at least one dose of atorvastatin. If the trial can continue after 40 patients, then interim analyses will be complete. Adverse events will continue to be recorded and reported for all patients. If the toxicity or efficacy rates are noted to be different among the patient subgroups, the same stopping rules may be applied to any subgroup of concern to discontinue enrollment of that subgroup.

A Bayesian sequential monitoring design (Thall et al. 1995 and 1998) will be used to monitor the trial for toxicity and futility. Calculations were performed in MultcLean 2.1.

Toxicities will be monitored assuming a prior probability of toxicity following Beta(1,1) against a constant rate of 30% as the maximum acceptable toxicity rate. Trial limiting toxicities (TOX) are any grade 3 or higher toxicities at least possibly related to the study drug that occur in the first 8 weeks of therapy. The trial will be terminated if  $\text{Prob}(\text{TOX} > 0.30 \mid \text{data}) > 0.95$ . Following this rule, the trial will be terminated according to the table below once the first 10 patients have enrolled.

Similarly, efficacy will be monitored assuming a prior probability of response following Beta(0.33,0.67) against a constant rate of 33% as the minimum acceptable response rate. A patient will have a response if there is documented improvement at any time point on the trial. The trial will be terminated if  $\text{Prob}(\text{Response} < 0.33 \mid \text{data}) > 0.975$ . Following this rule, the trial will be terminated according to the following table once the first 10 patients have enrolled.

If there are this many patients treated who are evaluable (i.e., have TOX or completed the first 8 weeks without TOX for TOX, or have at least one IIEF result post-baseline for response)	10	20	30	40

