Stop the trial if there are this many (or more) patients who have TOX	6	10	14	17
Stop the trial if there are this many (or fewer) patients who have responded.	0	2	5	7

The first 10 patients will be accrued before the first analysis. If 6 or more of the 10 patients have TOX events, stop the trial and the treatment will be declared as too toxic for this population. If there are 5 or fewer patients with TOX events and at least 1 patient with response, enroll the

next 10 patients and compare the number of patients with TOX and response against the table's rules.

The futility rule will be checked at the same time as the safety check even though the assessment time is later. As long it is safe and there are enough responses to continue, the trial will continue without delay. If there are not enough responses to continue but enough patients are pending response that it will be possible to continue once they are assessed, enrollment will hold until enough responses occur or enough patients go off study without response to prevent the possibility of passing the rule. Since response can occur at any of the planned times, a patient who was previously a non-responder can become a responder at a later follow-up and will count as a responder in the current analysis even if counted as non-responder in a previous analysis. A patient will not change from a responder to non-responder later.

The operating characteristics for these rules are summarized in the following table, based on simulations performed in Multc Lean Desktop version 2.1.

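### Section 11.D does not say whether a toxicity look waits for men still in the 8-week window, and it holds enrolment only for pending responses

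*Combined protocol and SAP*

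**What the plan says.** All of this is in section 11.0, part D, unless noted.

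- **What TOX is:** "any grade 3 or higher toxicities at least possibly related to the study drug that occur in the first 8 weeks of therapy". A man without an event is therefore classified only after 8 weeks.
- **Look trigger by enrolment:** "Interim analyses will begin after 10 patients have been enrolled", and "the trial will be terminated according to the table below once the first 10 patients have enrolled".
- **Look trigger by evaluability:** the header of the boundary table counts men who "have TOX or completed the first 8 weeks without TOX for TOX, or have at least one IIEF result post-baseline for response". Part E likewise asks for an efficacy/safety summary per 10 evaluable men with 8 weeks of treatment.
- **Short treatment:** "Patients who receive treatment less than 8 weeks will still be counted in toxicity and futility monitoring as long as they received at least 1" (a single administration is enough). The sentence does not say whether this means only men who stopped early, or also men still on treatment in the window.
- **Pending responses:** if men awaiting assessment could still rescue the futility decision, "enrollment will hold until enough responses occur or enough patients go off study without response to prevent the possibility of passing the rule".
- **Pending TOX:** no matching sentence. Otherwise, "As long it is safe and there are enough responses to continue, the trial will continue without delay".

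**The concern.** The authors saw that an outcome can be pending at a look and wrote a hold for it, but only for response. The response hold prevents a premature futility stop. Nothing equivalent prevents a missed or late safety stop.

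With the trigger stated two ways, two open-accrual readings are possible. Under one, the look comes at the nth enrolment, before the most recent men have had time to show TOX. Under the other, the look waits for n evaluable men while further men start treatment. The first weakens the rule. The second exposes more men than the table shows. Only the looks at 20, 30 and 40 are affected from here on: part A records 11 men enrolled at the 2021 revision and the first look passed.

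**Working it through.** **Inputs from section 11.D.** "Toxicities will be monitored assuming a prior probability of toxicity following Beta(1,1) against a constant rate of 30% as the maximum acceptable toxicity rate"; stop if Pr(TOX > 0.30 | data) > 0.95. Response prior Beta(0.33, 0.67); stop if Pr(response < 0.33 | data) > 0.975. Looks at 10, 20, 30 and 40; N = 50; TOX window 8 weeks.

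**Assumptions.** The documents give no accrual rate and no TOX onset times. Section 1.0 gives 50 men, 4 years in total and 1 year of participation. If accrual takes the remaining 36 months, the rate is 50/36 ≈ 1.4 men a month; 1 to 2 is shown as the range. Onset is taken as uniform over the 8 weeks, with alternatives below. Eight weeks is 8/4.345 = 1.84 months.

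**Step 1: boundaries.** With k TOX among n men the posterior is Beta(1 + k, 1 + n − k). At n = 20, k = 10 gives Pr(TOX > 0.30) = 0.974 and k = 9 gives 0.932, so the boundary is 10. The same calculation gives 6, 10, 14 and 17 for TOX, and the response posterior gives 0, 2, 5 and 7. All match the plan.

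**Step 2: the plan's own table.** Exact binomial recursion over the four looks, with every outcome known at each look, gives toxicity-rule stop probabilities of 0.116, 0.508 and 0.892 at true TOX 0.30, 0.40 and 0.50. The futility rule stops with probability 0.063 at response 0.33. Combined as 1 − (1 − P_tox)(1 − P_resp):

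- 0.30/0.33: 1 − 0.884 × 0.937 = 0.17 (plan 0.17)
- 0.40/0.33: 1 − 0.492 × 0.937 = 0.54 (plan 0.54)
- 0.50/0.33: 1 − 0.108 × 0.937 = 0.90 (plan 0.90)

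All 25 rows reproduce within 0.005. The table therefore describes a design with nobody pending.

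**Step 3: look at the nth enrolment, pending men counted as TOX-free so far.** At 1.4 men a month, about 1 + 1.4 × 1.84 = 3.6 of the n men are still in the window. Simulated stop probability, toxicity rule alone, Poisson accrual:

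| True TOX | All known | 1/month | 1.4/month | 2/month |
|---|---|---|---|---|
| 0.40 | 0.51 | 0.39 | 0.37 | 0.34 |
| 0.50 | 0.89 | 0.82 | 0.80 | 0.78 |

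- Onset timing, 1.4 a month, TOX 0.40: 0.42 if events fall in weeks 0–2, 0.31 if in weeks 6–8.
- Looks at 20, 30 and 40 only (not conditioned on the observed data), 1.4 a month, TOX 0.40: 0.36 against 0.48.
- Both rules together, response 0.33 visible at 3 months, written response hold applied, 1.4 a month: about 0.42 and 0.82 at TOX 0.40 and 0.50, against the table's 0.54 and 0.90.

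**Step 4: look at n evaluable men, accrual open.** Stop probability is unchanged: 0.51 and 0.89. Mean extra men enrolled by each look is rate × 1.84: 1.8, 2.6 and 3.7 at 1, 1.4 and 2 a month. At true TOX 0.50 and 1.4 a month, the enrolled median (quartiles) under the toxicity rule alone is 22 (13, 35); the table gives 20 (10, 30) at response 0.33 and above.

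**Step 5: how often a TOX hold would bite.** With m men pending and boundary b, a hold occurs if b − m ≤ X ≤ b − 1, where X ~ Binomial(n − m, p). At n = 20, b = 10:

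- m = 3, p = 0.10: P(7 ≤ X ≤ 9), X ~ Bin(17, 0.10) = 0.1%
- m = 3, p = 0.30: 21%
- m = 7, p = 0.30: P(3 ≤ X ≤ 9), X ~ Bin(13, 0.30) = 80%

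At p = 0.30, n = 30 and n = 40 give 14% and 16% with 3 pending, and 56% and 54% with 7.

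**The case against.** The best defence is the boundary-table header. A man at week 3 without TOX is not evaluable by that definition, so he cannot fill one of the 20, 30 or 40 places. The evaluable-patient summary in part E, which goes to the IND Office for review and approval, points the same way. Part D also makes enrolment of the next ten follow from an acceptable first look. Taken together, these could mean that the next ten wait for an evaluable look, and that would deliver the table in full. This reading can be argued, but no sentence states the wait, and the enrolment triggers and the no-delay sentence pull against it.

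A reader might infer that the stated stopping probabilities are not delivered whichever way the plan is read, or that the table is miscalculated. The documents support neither. The table reproduces, and its probabilities fail only if looks are taken before TOX is known.

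The response hold gives some incidental cover. The first post-baseline IIEF-5 is at 3 months (Table 1), after the TOX window, so a response hold also lets TOX mature. At an assumed 4 men a month it lifts toxicity stops from 0.25 to 0.32 at true TOX 0.40, and from 0.68 to 0.75 at 0.50. At 1 to 2 a month it changes little. It ends once enough responders are seen, so it does not replace a TOX hold.

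It is also fair to say that section 2.0 calls the agents generally well tolerated, and that grade 3 events already trigger individual action under section 8.0 and SAE reporting under section 10.0. Those protect the individual man; they do not settle when the trial-level rule is applied. The 0.40 and 0.50 scenarios are the plan's own.

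**Conclusion.** The point holds as a gap in specification with a measurable consequence; it is not a proven wrong figure. What the plan delivers depends on a choice it does not make:

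- **Looks at the nth enrolment:** the toxicity rule loses about 14 points of stopping probability at true TOX 0.40 (0.51 to 0.37) and 9 at 0.50 (0.89 to 0.80), at 1.4 men a month with uniform onset. Over 1 to 2 a month the values are 0.34–0.39 and 0.78–0.82.
- **Looks at n evaluable men, accrual open:** the probabilities stand, but 1.8 to 3.7 extra men per look enrol at 1 to 2 a month, and the sample-size column is not delivered.
- **Next ten wait for an evaluable look:** the table is delivered, but the plan does not say this.

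The sizes rest on the assumed accrual rate and onset pattern. The missing hold and the double trigger rest on the text alone. The documents do not say how the first look was timed, so nothing here shows that it was wrong. This should be changed because it concerns a safety rule and the remedy is cheap.

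**What to change.** In section 11.D:

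1. State that each toxicity look uses the first n TOX-evaluable men, and align the enrolment-based sentences with that.
2. Say whether the sentence on treatment shorter than 8 weeks covers only men who stopped early, and reconcile it with the evaluable definition.
3. Add a hold for the looks at 20, 30 and 40, for example: *When n men have been enrolled, if the men with TOX plus the men still within their first 8 weeks could reach the boundary (10 of 20, 14 of 30, 17 of 40), enrolment pauses until the boundary can no longer be reached, or is reached and the trial stops. Otherwise enrolment continues.* The boundaries are the plan's own, and each decision is then the one made with all outcomes known, so both columns of the table apply.
4. If the sponsor prefers to keep accrual open, re-simulate the operating characteristics with the expected accrual rate and the 8-week delay.

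The cost is a few sentences and pauses of up to about 8 weeks. Pauses are uncommon when TOX is low and few men are pending (0.1% at n = 20 with 3 pending and TOX 10%). They become frequent as either rises (21% with 3 pending and 80% with 7 pending, at TOX 30%). Seven pending corresponds to roughly 3 men a month (1 + 3 × 1.84 = 6.5), about twice the rate implied by the trial's stated duration.

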**E. Modification of Vitamin E dosing:**

1. If toxicity is Grade 2, decrease dosage by 50%. If toxicity resolves or decrease to Grade 1, maintain Vitamin E at this lower dose. If toxicities are  $\geq$ Grade 3, stop Vitamin E and the patient should be removed from the study.
2. Discontinue if signs or suspicion of cardiovascular issues appear.

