**G. Modification of drug dosing where side effect can't be attributed to one specific drug:**

1. Since the 3 study drugs have overlapping toxicities, circumstances may arise in which it is not clear which drug is responsible for the toxicity.
2. If the toxicities are  $\geq$ Grade 3, stop all 3 drugs and the patient should be removed from the study.
3. If toxicity is Grade 2, first reduce the dose of atorvastatin as per guidelines above. If after 1 week the toxicity has not decreased to Grade 1 or resolved, reduce the dose of Pentoxifylline as per guidelines above. If after an additional week the toxicity has not decreased to Grade 1 or resolved, reduce the dose of Vitamin E as per guidelines above. If after another week the toxicity has not resolved or decreased to Grade 1, all 3 drugs should be stopped and the patient should be removed from the study.

4. Cardiovascular issues: for toxicity of Grade 3 or higher, all 3 drugs will be discontinued, and the patient directed to the nearest emergency department for urgent evaluation. For toxicity of Grade 2, guidelines delineated in sections 8.G.1-3 above will be followed for drug dosing modifications, while concurrently obtaining a cardiovascular evaluation from the patient's cardiologist (if he has one), or his personal primary care physician. At the patient's preference, cardiology evaluation may be obtained at MD Anderson. Continuation on study medications will be contingent on cardiology approval.

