## **B. Endpoints**

### **i. IIEF-5 (International Index of Erectile Function)**

This validated instrument will be completed as per study calendar. The instrument categorizes ED severity into 5 categories as none (22-25), mild (17-21), mild to moderate (12-16), moderate (8-11), or severe (5-7). A patient will demonstrate improvement at any time point if his score goes up enough to move at least 1 category less severe compared to baseline. A patient with improvement will be considered to have a response. Patients who drop out of the trial without any measurements will count as a non-responder.

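### The operating-characteristics table matches a calculation with TOX and response independent, but the plan's rules generally remove a man with TOX before he can respond, so the stated stopping probabilities do not describe those rules

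*Combined protocol and SAP*

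**What the plan says.** Section 11.0 D monitors two endpoints together at 10, 20, 30 and 40 patients, with a maximum of 50. For toxicity: "Toxicities will be monitored assuming a prior probability of toxicity following Beta(1,1) against a constant rate of 30% as the maximum acceptable toxicity rate". For futility: "efficacy will be monitored assuming a prior probability of response following Beta(0.33,0.67) against a constant rate of 33% as the minimum acceptable response rate". The table of operating characteristics then lists the probability of stopping early for 25 pairs of true TOX and response rates, and is introduced by: "The operating characteristics for these rules are summarized in the following table, based on simulations performed in Multc Lean Desktop version 2.1". The association assumed between the two endpoints is not given.

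Four other places bear on that association.

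- TOX is a related Grade 3 or higher event, and only events "that occur in the first 8 weeks of therapy" count.
- Sections 8.0 D to 8.0 G deal with Grade 3 or higher toxicity. For Vitamin E the instruction is to "stop Vitamin E and the patient should be removed from the study". Atorvastatin (for its listed side effects) and pentoxifylline have matching wording. When the responsible drug is unclear, it is to "stop all 3 drugs and the patient should be removed from the study".
- Table 1 has no IIEF-5 at 6 weeks. The first after baseline is at 3 months, plus or minus 2 weeks, and response must be documented on the trial.
- Section 11.0 B.i: "Patients who drop out of the trial without any measurements will count as a non-responder". Section 11.0 D also keeps men treated for under 8 weeks in the futility count. The header of the stopping table instead requires a post-baseline IIEF result before a man is evaluable for response.

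**The concern.** TOX is settled by week 8 and normally ends participation. Response cannot be measured before about week 11 (3 months less 2 weeks). The two events should therefore seldom occur in the same man. A simulation that treats them as independent lets many men be both: in the bold row (0.30/0.33) the share is 0.30 x 0.33 = 9.9%.

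This table is the plan's only account of how often the rules stop a poor treatment or wrongly stop an acceptable one. If its joint distribution is not the one the rules create, the figures belong to a different design. A reader also cannot tell whether the tabulated response rate refers to all treated men or to those still on study to be assessed.

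**Working it through.** **Inputs.** Priors and thresholds are from Section 11.0 D: TOX Beta(1,1) against 0.30, stop above 0.95; response Beta(0.33, 0.67) against 0.33, stop above 0.975. The boundaries are from the stopping table: TOX at or above 6/10/14/17, responders at or below 0/2/5/7.

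**Step 1: boundaries.** With x events in n men, the posteriors are Beta(1+x, 1+n-x) and Beta(0.33+x, 0.67+n-x). All eight boundaries reproduce. For example, 10 TOX in 20 gives 0.974 and 9 gives 0.932; 2 responders in 20 gives 0.993 and 3 gives 0.971.

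**Step 2: the plan's own table.** Let pT and pR be the true rates. An exact recursion on the joint count (TOX, responders), in blocks of 10 with a stopping check at each look, was run with Pr(TOX and response) = pT x pR. All 25 stated probabilities are matched within 0.005, and the medians and quartiles also agree. Examples: 0.30/0.33 gives 0.172 (stated 0.17); 0.40/0.25 gives 0.644 (0.64); 0.50/0.15 gives 0.980 (0.98). Independence is inferred from this agreement; the plan does not state it.

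**Step 3: no overlap, same marginal rates.** The four cells become: both, 0; TOX only, pT; response only, pR; neither, 1 - pT - pR. This counts TOX men as non-responders and reads pR as the whole-cohort rate.

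| TOX / response | Stated | No overlap | Difference (points) |
|---|---|---|---|
| 0.30 / 0.15 | 0.84 | 0.823 | 1.7 |
| 0.40 / 0.15 | 0.91 | 0.871 | 3.9 |
| 0.50 / 0.15 | 0.98 | 0.955 | 2.5 |
| 0.30 / 0.25 | 0.36 | 0.334 | 2.6 |
| 0.40 / 0.25 | 0.64 | 0.585 | 5.5 |
| 0.50 / 0.25 | 0.92 | 0.898 | 2.2 |
| 0.30 / 0.33 | 0.17 | 0.158 | 1.2 |
| 0.40 / 0.33 | 0.54 | 0.517 | 2.3 |
| 0.50 / 0.33 | 0.90 | 0.892 | 0.8 |

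Fifteen other rows stay within 0.006 of the stated value. In the remaining row, 0.50 + 0.55 = 1.05, which is impossible with no overlap. It needs an overlap of at least 0.05, that is 0.05/0.50 = 10% of TOX men responding.

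**Step 4: implied rate in TOX-free men.** With no overlap this is pR/(1 - pT): 0.33/0.70 = 47% in the bold row and 0.45/0.50 = 90% in the 0.50/0.45 row.

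**Step 5: the other meaning of the response rate.** Assume instead that the tabulated rate applies to TOX-free men and that TOX men are non-responders, so the whole-cohort rate is (1 - pT) x pR. At response 0.33, the probability of stopping early is 0.122 for TOX 0.10 (table 0.06), 0.225 for 0.20 (0.07) and 0.412 for 0.30 (0.17). At 0.40/0.25 it is 0.871 (0.64).

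**Step 6: the stopping-table header.** Leave TOX men out of the response denominator, apply the tabulated rate to the rest, and evaluate the futility rule on the reduced number. Results then move both ways: 0.30/0.15 gives 0.757 (table 0.84) and 0.30/0.33 gives 0.206 (0.17).

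**Step 7: partial removal.** Assume 80% of TOX men are removed and the others respond like TOX-free men, with the whole-cohort rate kept. Then 0.40/0.25 gives 0.603 and 0.40/0.15 gives 0.882.

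**The case against.** Nothing in the table is miscalculated: it reproduces, it shows marginal rates, and it makes no claim about their association. That is correct. The fault is an unstated assumption that does not fit the rules.

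A reader might infer that a man with TOX can never respond. The documents do not go that far. For transaminase and CK thresholds (8.0 D.1 and D.2) the text says only to discontinue the statin. For Grade 3 or higher cardiovascular toxicity (8.0 G.4) it calls for stopping the drugs and urgent evaluation. Neither states removal from the study. The plan gives no expected share of such events. It follows that the 0.50/0.55 row cannot simply be called impossible, since 10% of TOX men responding is enough to allow it.

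A reader might also infer that the table always overstates stopping. That needs two choices the documents leave open: TOX men counted as non-responders, and a whole-cohort response rate. Steps 5 and 6 show that other choices reduce, reverse or enlarge the difference.

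The effect in Step 3 is modest. Three of the nine differences are under 2 points, the bold row barely moves, and 0.50/0.15 still stops 95.5% of the time. No boundary changes. All of this stands and limits the weight of the point. It does not remove it, because none of the readings consistent with removal after TOX gives back the stated table.

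**Conclusion.** The point holds in a limited form. The table agrees with independence of TOX and response, while the removal rules and the IIEF-5 calendar mean that TOX generally precludes response. The stated stopping probabilities are therefore not those of the rules described.

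Size and direction depend on the reading. With TOX men as non-responders and a whole-cohort response rate, nine rows are too high by 0.8 to 5.5 points, all at TOX 0.30 or more and response 0.33 or less. With the rate read as that of TOX-free men, the table understates stopping, by 24 points at 0.30/0.33 (0.41 - 0.17). The latter matters more for interpretation, because TOX 0.30 is the maximum the plan accepts and 0.33 the minimum response it accepts. Neither a uniform overstatement nor an unconditionally impossible row is established. The stopping boundaries are sound as derived.

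**What to change.** 1. Reconcile Section 11.0 B.i and the Section 11.0 D text, which count men without a measurement or with under 8 weeks of treatment, with the stopping-table header, which makes men without a post-baseline IIEF not evaluable for response.
2. State the joint distribution of TOX and response used in the simulation, consistent with removal after TOX (zero or near-zero overlap). If it is not zero, say what share of TOX men is assumed to stay assessable.
3. Re-run the operating characteristics on that basis and replace the table.
4. Label the response column as the rate in all treated men, and put the implied TOX-free rate pR/(1 - pT) beside it.
5. Drop the 0.50/0.55 row only if the overlap is set to zero.

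The cost is one re-run, a replaced table and somewhat different stated probabilities. Sample size and the current boundaries stay as they are.
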